1.0 Investigational Plan

A multicenter clinical research study will be conducted in the United States and Canada. A total of 120 subjects will be enrolled with 60 subjects in each arm to compare the safety and efficacy of the Ex-PRESS mini glaucoma shunt implantation versus trabeculectomy in patients suffering from glaucoma.

2.0 Study Purpose

The purpose of this study is to compare the safety and effectiveness of the Ex-PRESS mini glaucoma shunt to trabeculectomy in reducing the number of post operative complications, reducing intraocular pressure (IOP) and reducing the use of hypotensive medications in subjects with open-angle glaucoma or ocular hypertension.

3.0 Rationale for the Study

Trabeculectomy has been the surgical treatment of choice for primary open angle glaucoma since 1970s (1), its success rates and complications however are less than ideal. Early hypotony and bleb infections are still of concern.

The Ex-PRESS, a miniature stainless steel glaucoma device approved by FDA since March 2002, is widely used worldwide for open angle glaucoma patients. This procedure is theoretically more reproducible and simple to perform as well as less traumatic to the ocular tissue than traditional filtering surgery.

With regard to the inclusion of subjects diagnosed and being treated for ocular hypertension, several recently published studies demonstrate that in patients with elevated IOP, with or without the visual field loss or optic nerve damage of glaucoma, lowering IOP provides benefit in long-term outcome of subsequent visual field loss (2-5). In any case, all subjects enrolled in the study have the opportunity to be treated with ocular hypotensive medications during the follow-up period as judged appropriate by the investigator.

4.0 Potential Risks and Benefits

The potential risks with the use of the Ex-PRESS are the same, with the same probability of occurrence and of the same magnitude, as would be found with conventional glaucoma drainage surgery. They include a risk of bleeding, infection, too low an intraocular pressure after surgery, failure of the operation to control the intraocular pressure, corneal swelling, risk of implant erosion, and double vision.

The following potential benefits have been identified:

- If the implant is effective and reduces intraocular pressure, the subject may reduce or eliminate glaucoma medication therapy.
- If the implant is effective and reduces intraocular pressure, the subject may not require additional glaucoma surgery.

- If the subject requires additional glaucoma surgery post Ex-PRESS implantation, this option requires a smaller conjunctival incision than trabeculectomy, therefore sparing more conjunctival tissue..
- This procedure is less invasive than other conventional glaucoma surgeries, thus resulting in potentially fewer complications.

5.0 Background

Glaucoma filtering surgery is indicated when glaucomatous damage progresses despite the attempt to lower the intraocular pressure (IOP) obtained with pharmacological and/or laser treatment. In the past few years, filtering surgery has improved, with an increased likelihood of successfully lowering the IOP while minimizing complications. While full thickness filtration procedures considerably reduced the IOP, they were associated with early postoperative hypotony and related side effects and became progressively less popular. Trabeculectomy has been the surgical treatment of choice for open angle glaucoma (OAG) since the 1970s; its success rate and complication rate however are less than ideal. Early hypotony and bleb infections are still of concern.

The Ex-PRESS is a miniature stainless steel glaucoma device, developed as an alternative to trabeculectomy and to the other types of glaucoma filtering surgery for patients with OAG. The Ex-PRESS mini glaucoma shunt is FDA approved since March 2002. This procedure is theoretically more reproducible and simple to perform as well as less traumatic to the ocular tissue than traditional filtering surgery.

5.1 Clinical Studies

Since the Ex-PRESS mini glaucoma shunt was FDA approved, post marketing studies were performed and presented in paper publications and meetings (1, 6-20). The Ex-PRESS was found to be safe and effective in the treatment of glaucoma subjects. A prospective randomized study comparing the Ex-PRESS to trabeculectomy in open angle glaucoma patients was performed in the Netherlands. A total of 40 subjects with primary open angle glaucoma were enrolled in each study arm and followed for 1 year. The Ex-PRESS implant under a scleral flap was found to have a more effective success rate, % IOP reduction and medication reduction compared to trabeculectomy (20).

6.0 Device Description

The Ex-PRESS is a miniature drainage device designed to regulate intraocular pressure in eyes suffering from glaucoma. The concept behind the Ex-PRESS is to divert aqueous humor through the implant from the anterior chamber to an intrascleral space - the bleb. The Ex-PRESS glaucoma implant is manufactured from implantable stainless steel. It consists of a 2-3 mm long and 0.4mm outer diameter and 50 micron inner diameter tube, which connects the anterior chamber to the intrascleral space. Despite its miniature size, the Ex-PRESS features several major structural elements (figure 1):

1. A cannula for draining aqueous humor from the anterior chamber to the intrascleral space.
2. A plate to prevent excessive penetration.
3. A spur to prevent extrusion of the Ex-PRESS™ from the eye.

4. Reserve orifices near the distal end, which constitute an alternative conduit for aqueous humor drainage in case of occlusion of the primary (axial) opening of the cannula by the iris.

[figure not shown]

Figure 1: Ex-PRESS

The Ex-PRESS is loaded on a specially designed disposable introducer. The introducer has a female Luer Lock base and mounted on a disposable 1 ml syringe.

7.0 Study Objective

The study objective is to compare the safety and effectiveness of Ex-PRESS implantation under a scleral flap versus trabeculectomy.

7.1 Primary Effectiveness End Points

The primary effectiveness measure will be qualified and complete success rate defined as $IOP \leq 18 \text{ mmHg}$ with or without medications in the test group as compared to complete and qualified success rate in the concurrent control group at 12 months.

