7.2 Secondary Effectiveness End points

The secondary effectiveness measure will be qualified and complete success rate defined as $IOP \leq 18 \text{ mmHg}$ with or without medications in the test group as compared to qualified and complete success rate in the concurrent control group at 24 months.

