7.3 Primary Safety End Points

Post operative safety profile defined as vitreous loss and hypotony ($IOP \leq 5 \text{ mmHg}$) and related complications (choroidal effusion, hyphema, shallow/flat AC, leaking bleb).

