9.6 Follow up

All subjects will participate in defined follow-up visits for two years. Follow up visits include day of surgery, day 1, 1-2 Weeks, Months 1, 3, 6, 12, 18 and 24 post surgery. Additional visits will be performed and recorded as required for the optimal treatment and follow up of the patient. Additional visits are defined as visits that were not preplanned and considered emergent. Table 1 presents the activities to be performed at each follow up visit.

Table 1: Follow-up Activities

Activity	Screening	Surgery	1 Day	1-2 Wk	1 Mo	3 Mo	6 Mo	12 Mo	18 Mo	24 Mo
Ophthalmology Exam	X									
Medical History	X									
Medication Assessment	X		X	X	X	X	X	X	X	X
Visual Field	X							X		X
CD ratio	X							X		X
Slit-lamp Exam	X		X	X	X	X	X	X	X	X
Visual Acuity	X		X	X	X	X	X	X	X	X
Fundus Exam	X							X		X
IOP	X		X	X	X	X	X	X	X	X
Procedure		X								
Adverse Event Assessment		X	X	X	X	X	X	X	X	X
Protocol Deviation Assessment		X	X	X	X	X	X	X	X	X

- Intraocular pressure measurements during follow-up visits

Each time IOP is measured, the surgeon or technician is to utilize a Goldmann tonometer, however, an independent observer should read the measurement and then record the measurement to minimize observer bias.

Two measurements should be taken and the mean recorded on the case report form UNLESS they differ by more than 2 mmHg in which case a third measurement is taken and the median value is recorded.

All attempts should be made to conduct each follow-up evaluation within the specified time intervals (Table 2).

Table 2: Follow up examination schedule

Follow up visit	Acceptable Time Interval (Days from Procedure)
Day 1 pos-op	Day 1 post op
7-14 days post-op	7-14 days post-op
1 month post-op	30 days \pm 7 days
3 months post-op	90 days \pm 14 days
6 months post-op	180 days \pm 21 days
12 months post-op	360 days \pm 30 days
18 months post-op	540 days \pm 30 days
24 months post-op	720 days \pm 30 days

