9.7 Study Withdrawal

All subjects have the right to withdraw at any point during the treatment without prejudice. The investigator can discontinue any subject at any time if medically necessary. If a subject withdraws prematurely from the study, a genuine effort must be made to determine the reason(s) why the subject discontinued the study. The reason must be recorded.

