12.0 Statistical Analysis

The data provided from this randomized controlled study are intended to provide a reasonable assurance of safety and effectiveness for the Ex-PRESS mini shunt compared to standard trabeculectomy.

The primary safety and effectiveness end points are provided in sections 7.1-7.4 of this protocol. The data will be analyzed using the Fishers exact test p-value and Student's paired *t* test p-value comparison. Success rate will be analyzed using Kaplan-Meier survival analysis curves. [Phakic and pseudophakic patients will be explored as a possible covariate in the efficacy and safety analysis.](#)

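### Success in 7.1 and 7.2 is judged on IOP alone, so a re-operated eye can count as a success of the assigned operation; the Section 12 Kaplan-Meier event is not fully defined.

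*Combined protocol and SAP*

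**What the plan says.** **Efficacy.** Section 7.1 sets the threshold for success at an IOP of 18 mmHg or less. It introduces this with "The primary effectiveness measure will be qualified and complete success rate defined as". The comparison between arms is then worded "with or without medications in the test group as compared to complete and qualified success rate in the concurrent control group at 12 months". Section 7.2 opens in the same way, "The secondary effectiveness measure will be qualified and complete success rate defined as", with the same threshold at 24 months. Neither has a lower limit or mentions further surgery.

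**Safety.** Section 7.3 puts low pressure in the primary safety end point: "Post operative safety profile defined as vitreous loss and hypotony", with hypotony set at 5 mmHg or below. Section 7.4 compares all adverse events between arms, and 11.1 makes the need for surgical intervention a criterion of seriousness.

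**Re-operation.** Section 4.0 lists it as something that an effective device may avert: "If the implant is effective and reduces intraocular pressure, the subject may not require additional glaucoma surgery". No section gives a re-operated eye an efficacy class.

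**Follow-up.** Section 9.6: "All subjects will participate in defined follow-up visits for two years". Section 9.7: "The investigator can discontinue any subject at any time if medically necessary".

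**Analysis.** Section 12: "Success rate will be analyzed using Kaplan-Meier survival analysis curves". Fisher's exact test and a paired t test are also named, but for the data in general rather than for a given end point.

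**The concern.** Section 8.0 claims efficacy on a par with trabeculectomy. That comparison is meant to reflect what the assigned operation achieves. If a second operation can turn a failed eye into a success, the rate describes the assigned operation plus whatever followed it. The arms can then look alike although one needed more re-operations, or look different for reasons unrelated to the first procedure.

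The Kaplan-Meier sentence does not close the gap. A curve needs an event, a first reading that can trigger it, a rule on confirmation and a censoring rule. With these open in an unmasked trial, several defensible success rates can be drawn from the same data, and the choice can be made after results are seen.

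**Working it through.** **1. Four eyes set against the text at month 12**

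| Eye | 7.1 read literally | Elsewhere |
|---|---|---|
| 14 mmHg after the assigned operation alone | Success | – |
| 14 mmHg after a second glaucoma operation, still followed (9.6) | Success | If the surgery was for a complication: serious adverse event (11.1), counted in 7.4 |
| Re-operated, then discontinued by the investigator (9.7) | No 12-month IOP, no stated class | As above |
| 4 mmHg | Success | Primary safety event (7.3) |

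The first two eyes score the same. The second and third had the same course up to re-operation, but whether they have an efficacy class depends on a decision about discontinuation.

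**2. Does Kaplan-Meier settle it?** The natural event is the complement of success, IOP above 18 mmHg. On that reading a re-operated eye fails only if a qualifying reading above 18 mmHg was recorded beforehand. An eye re-operated for another reason, or between scheduled visits, may never meet the event. Table 1 schedules 6 post-operative IOP visits to month 12 (day 1, weeks 1-2, months 1, 3, 6, 12) and 8 to month 24. Nothing says which of them count.

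**3. Size of one reclassified eye.** With 60 per arm (9.3.1), 1/60 = 1.67 points. For scale only, assume 51/60 successes in each arm as written, then a net 0, 1 or 3 eyes reclassified in one arm. The 95% interval is the difference ± 1.96 × √[p1(1−p1)/60 + p2(1−p2)/60].

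- 51/60 v 51/60: 0.0 points (−12.8 to 12.8)
- 51/60 v 50/60: 1.7 points (−11.4 to 14.7)
- 51/60 v 48/60: 5.0 points (−8.6 to 18.6)

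Signs reverse if the other arm is affected. Every interval includes 0, and the plan states no margin, so none of these shows a changed conclusion.

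**4. Visit proportion or Kaplan-Meier estimate.** Keep the same assumed base: a 15% chance of IOP above 18 mmHg at each visit, so 85% success at the 12-month visit. Let any single high reading be the event.

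- Readings count from month 3 (3 visits): event-free success lies between 0.85³ = 61.4% (independent readings) and 85% (fully dependent).
- Readings count from day 1 (6 visits): between 0.85⁶ = 37.7% and 85%.

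A simulation with equally correlated normal readings (within-eye correlation 0.4 to 0.8) gives 67.5 to 75.5% from month 3 and 53.2 to 69.2% from day 1. Requiring two consecutive high readings from month 3 gives 88.6 to 92.4%. These inputs are assumed. The point is only that the first qualifying visit and the confirmation rule can move the reported rate well away from 85%, in either direction.

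**The case against.** **Low pressure already has a home.** Section 7.3 makes hypotony a primary safety event, and 8.0 makes separate claims for safety and efficacy. Keeping low pressure in one and pressure control in the other is a coherent design, and a lower limit would count late hypotony in both. This stands. A reader might infer that the plan ignores hypotony, but 7.3 counts it against its arm. The overlap is therefore the secondary part of this point.

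**Re-operations are visible.** Those done for complications would appear as serious adverse events and in the 7.4 comparison. This also stands, and it narrows the gap: what is missing is the efficacy class, not the record. The discontinued eye is a possibility rather than a planned path, since 9.7 does not make re-operation a reason to discontinue.

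**The 12-month rate may not be a single-visit proportion.** A reader might infer from 7.1 that it must be. Section 12, however, ties Kaplan-Meier to the success rate by name, so the rate could equally be the Kaplan-Meier estimate at 12 months. The documents support neither reading over the other, and that ambiguity is part of the point.

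**The failure event is half given.** IOP above 18 mmHg follows from the success rule. The first qualifying visit, confirmation, re-operation and censoring do not.

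**Conclusion.** The point holds and should be fixed. Followed literally, 7.1 and 7.2 credit the assigned operation with pressure achieved by a later one. This distorts the comparison claimed in 8.0 to the extent that the number of such eyes differs between arms. Section 12 neither defines its event in full nor says which 12-month rate is primary. The double role of an eye at 5 mmHg or below is a lesser matter of scoring, to be stated in advance.

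A reader might go further and infer that the definition favours one arm or would overturn the trial's conclusion. The documents do not support that. They give no re-operation or late hypotony rates, so direction and size are unknown, and equal numbers in both arms cancel in the difference. The only firm figure is 1.7 points per reclassified eye, taking all 60 subjects per arm as analysed. The 51/60 base, the net 0 to 3 eyes and the 15% per-visit probability are assumptions for scale.

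**What to change.** (a) In 7.1 and 7.2, add the condition that the study eye has had no further glaucoma surgery since the index procedure. Count re-operated eyes as failures in their randomised arm, whether or not they are later discontinued. List the procedures that count, starting from the glaucoma surgery list in 9.3.4, and say whether bleb or flap revision and laser procedures are included.

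(b) State whether the primary 12-month rate is the proportion at the visit or the Kaplan-Meier estimate.

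(c) In Section 12, define the Kaplan-Meier event as re-operation, at its date, or IOP outside the success range from a stated first visit, with a stated confirmation rule. Censor other withdrawals at their last IOP visit.

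(d) Report success both with and without a lower limit of IOP above 5 mmHg (the 7.3 threshold). The sponsor should state in advance which is primary, because the limit makes late hypotony count in both efficacy and safety.

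**Cost.** This is end point and analysis wording. Table 1 already schedules IOP and medication assessment at months 12 and 24. The form fields are not shown, so confirm that CRF 3 or CRF 4 captures re-operations with their dates. Under (a), and under (d) with the lower limit, success rates at the visit will be equal or slightly lower than under the present wording.

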7.2 Secondary Effectiveness End points

The secondary effectiveness measure will be qualified and complete success rate defined as $IOP \leq 18 \text{ mmHg}$ with or without medications in the test group as compared to qualified and complete success rate in the concurrent control group at 24 months.

7.3 Primary Safety End Points

Post operative safety profile defined as vitreous loss and hypotony ($IOP \leq 5 \text{ mmHg}$) and related complications (choroidal effusion, hyphema, shallow/flat AC, leaking bleb).

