8.0 Study Claim

The safety of the Ex-PRESS™ is superior and efficacy as good as trabeculectomy in open angle glaucoma patients.

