9.0 Study Protocol

9.1 Study Synopsis

Title:	A prospective randomized multi-center study to compare the Ex-PRESS™ to trabeculectomy in patients with open angle glaucoma who failed medical treatment and for which filtering surgery is indicated
Protocol Number:	XVT-01
Number of Sites:	7 sites were approved.
Study Period:	2 year, 10 visits: Pre-operation, day of surgery, day 1, 1-2 Weeks, Months 1, 3, 6, 12, 18 and 24 post operation. Additional visits will be performed and recorded as required for the optimal treatment and follow up of the patient. Additional visits are defined as visits that were not preplanned and considered emergent.
Study design:	A prospective, two arm, active control, unmasked, randomized study
Objectives:	A prospective randomized trial to compare the safety and efficacy of the Ex-PRESS to trabeculectomy in patients with open angle glaucoma who failed medical or are allergic to medical treatment and for which filtering surgery is indicated
Control Arm	Subjects undergoing trabeculectomy with the use of Mitomycin C
Treatment Arm	Subjects undergoing Ex-PRESS Under Scleral Flap implantation procedure with the use of Mitomycin C
Subject Population:	Open angle glaucoma patient's candidates for filtering surgery. The patients may have a history of cataract phacoemulsification surgery.
Sample Size:	Total of 120 subjects with 60 subjects in each arm. Each site can enroll a maximum of 30 subjects and a minimum of 5 subjects for each study arm.
Follow-up duration:	2 years
Target enrollment period:	Up to 1 year

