11.0 Safety

At each visit, the ocular health of each subject will be assessed. The cornea, anterior chamber, trabecular meshwork, and implant location (if applicable) will be examined. If any abnormalities are observed, they are to be noted (type and location) within the case report forms.

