11.1 Adverse Events

Any ocular adverse events occurring during the trial whether they are considered to be device related or not must be documented in the subject's records. Date and time of the event, its severity, treatment (if any) and the assessed relationship of the event to the study will be recorded on CRF 4 Adverse Event Form. Conditions which exist at the time the subject is enrolled do not need to be recorded on the Adverse Event Form as adverse events unless they increase in severity during the study.

A brief overview of the differences between anticipated, unanticipated and serious adverse events is provided below:

- **Anticipated Adverse Events**

Anticipated adverse events include those that might reasonably be expected to occur in this study because they are associated with glaucoma surgical procedures.

- **Unanticipated Adverse Events**

Unanticipated adverse device effects (UADE) include any serious adverse effects on health or safety or any life-threatening problem or death caused by or likely directly related to the Ex-PRESS mini shunt or the placement of the Ex-PRESS mini shunt within the eye that are not typically associated with glaucoma surgical procedures.

- **Serious Adverse Events**

Serious adverse events include those events that require or prolong hospitalization, require surgical intervention, are sight or life-threatening or fatal, or result in significant disability or incapacity.

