11.2 Reporting Adverse Events

All serious adverse events (whether anticipated or unanticipated) must be reported to the reviewing IRB according to their guidelines given..

All adverse events should be documented by completing CRF 4, Adverse Event Form and a specific IRB AE form (if applicable).

Identification and collection of adverse event information will be the responsibility of the study investigator. The investigator will follow the Declaration of Helsinki in order to ensure the safety of all subjects.

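### Shallow/flat anterior chamber and hyphema enter the primary safety endpoint with no threshold, on the call of an unmasked investigator; 3 to 6 opposing miscalls per arm would make equal arms differ significantly

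*Combined protocol and SAP*

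**What the plan says.** Section 7.3 (Primary Safety End Points) names vitreous loss, hypotony (IOP of 5 mmHg or less) and "related complications (choroidal effusion, hyphema, shallow/flat AC, leaking bleb"). Only hypotony has a threshold. The section does not say whether the components form one composite or are compared one by one.

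Section 9.1 describes "A prospective, two arm, active control, unmasked, randomized study". Section 11.2 states that "Identification and collection of adverse event information will be the responsibility of the study investigator". No masked assessor or adjudication is described.

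Three provisions bear on recording:

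- Section 11.0, on the examination at each visit: "If any abnormalities are observed, they are to be noted (type and location) within the case report forms".
- Section 11.1, on the adverse event form (CRF 4): "Date and time of the event, its severity, treatment (if any) and the assessed relationship of the event to the study will be recorded". No severity scale is given.
- Section 9.6, on IOP: "an independent observer should read the measurement and then record the measurement to minimize observer bias". Section 9.4.2 has the same rule for baseline. Nothing comparable applies to slit-lamp findings.

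The comparison supports the claim in section 8.0: "The safety of the Ex-PRESS™ is superior and efficacy as good as trabeculectomy in open angle glaucoma patients". Section 1.0 sets the size: "A total of 120 subjects will be enrolled with 60 subjects in each arm". Section 12.0 names Fisher's exact test but gives no alpha, sidedness or expected event rate.

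**The concern.** Chamber depth after filtering surgery is a continuum, and a hyphema can be a trace or a layer. With no stated line, the examiner decides for each eye whether a mild finding is an event, knowing which operation was done. Section 4.0 also tells the examiner which way the sponsor expects the result to go, since it lists potentially fewer complications as a benefit of the device.

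Randomisation does not protect against labelling that differs by arm. The severity on CRF 4 exists only once an event has been declared, so it cannot recover a mild finding that was never called. At stake is a primary safety comparison behind a superiority claim. The IOP rule shows that the plan recognises observer bias, but it guards the numeric component and leaves the more subjective ones open.

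**Working it through.** **Plan's own figure.** The only design figure is 120 subjects, 60 per arm. It cannot be reproduced, because the documents give no alpha, power, expected rate or margin.

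**Inputs.** From the documents: 60 per arm (section 1.0) and Fisher's exact test (section 12.0). Assumed: two-sided 0.05, no dropout, the same true event rate in both arms (5% to 50%), and every relabelled eye free of any other counted component.

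**Step 1: opposing calls needed.** Start from *x* events of 60 in each arm. Remove *k* from the device arm and add *k* to the control arm, then test (*x* − *k*)/60 against (*x* + *k*)/60. The smallest *k* with p < 0.05:

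| True events per arm | *k* per arm | Device v control | p | p with one call fewer per arm |
|---|---|---|---|---|
| 3 (5%) | 3 | 0 v 6 | 0.027 | 0.21 (1 v 5) |
| 6 (10%) | 4 | 2 v 10 | 0.029 | 0.13 (3 v 9) |
| 9 (15%) | 5 | 4 v 14 | 0.019 | 0.071 (5 v 13) |
| 12 (20%) | 5 | 7 v 17 | 0.039 | 0.11 (8 v 16) |
| 18 (30%) | 6 | 12 v 24 | 0.028 | 0.072 (13 v 23) |
| 24 (40%) | 6 | 18 v 30 | 0.040 | 0.093 (19 v 29) |
| 30 (50%) | 6 | 24 v 36 | 0.044 | 0.10 (25 v 35) |

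So 3 to 6 calls per arm are needed, which is 6 to 12 eyes in total, all miscalled in the device's favour.

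**Step 2: shift in one arm only, from 12 v 12.**

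- Five eyes added in control: 12 v 17, p = 0.39.
- Five eyes not called in the device arm: 7 v 12, p = 0.32.
- Control arm alone: 22 is not enough (12 v 22, p = 0.067) and 23 is (12 v 23, p = 0.044), so 23 − 12 = 11 eyes.
- Device arm alone: 4 v 12 gives p = 0.058 and 3 v 12 gives p = 0.025, so 12 − 3 = 9 eyes.

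**Step 3: chance of a false significant device advantage.** This is the sum of binomial probabilities over all tables with p < 0.05 in the device's favour, with event probabilities *p* − *s*/60 (device) and *p* + *s*/60 (control), where *s* is the expected number of shifted calls per arm.

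| True rate | No shift | 3 per arm, opposing | 5 per arm, opposing | 5 removed from device arm only |
|---|---|---|---|---|
| 10% | 1.1% | 33% | 85% | 31% |
| 20% | 1.4% | 20% | 55% | 17% |
| 40% | 1.6% | 15% | 39% | 11% |

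The no-shift column assumes equal rates in both arms, however high or low. Loose calling that affects both arms alike stays in that column, at under 2%.

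**The case against.** The strongest reply is that the arithmetic is a worst case. Moving 12 v 12 to 7 v 17 takes ten misclassified eyes, all in one direction: five of twelve device events (42%) go uncalled and five are added in control. Nothing in the documents shows that this would happen. That stands. The table in step 1 measures vulnerability and is not a forecast.

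A second reply is that hypotony is numeric and read by an independent observer. If the endpoint is a composite, an eye already counted for hypotony is unaffected by a chamber or hyphema call. This also stands, and it is why the counts apply only to eyes with no other component. Section 7.3 does not settle whether there is a composite. If components are tested singly, a rare one (3 of 60) needs only three opposing calls per arm.

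Two stronger readings are tempting:

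- *That no grade is recorded, so nothing can be repaired in analysis.* The documents do not support this. Section 11.0 does not say that type and location are all that is noted. CRF 4 takes severity and treatment, so declared events could be restricted to severe or treated ones. The fields of the follow-up form (CRF 3) are not shown and may include more. What remains is that the severity has no defined scale, is not used in the endpoint, and does not reach findings that were never declared.
- *That loose definitions alone would produce the claimed advantage.* They would not. The calling has to differ between arms.

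Counting any occurrence is also a legitimate choice. Restricting the endpoint to layered hyphema or to chamber loss beyond some level would narrow a primary safety measure and discard events, so it is not recommended here.

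**Conclusion.** The concern holds as a weakness in endpoint definition under unmasked assessment. Two components of the primary safety endpoint have no threshold, the person who decides whether they occurred knows the arm, and the safeguard against observer bias does not reach them.

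At 60 per arm, 3 to 6 opposing calls per arm would suffice for a significant device advantage across true rates of 5% to 50%. An expected shift of 3 per arm raises the chance of a false advantage from between 1% and 2% to between 15% and 33%. A shift in one arm only needs roughly twice as many calls.

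These figures rest on a two-sided 0.05 level, equal true rates, no dropout and relabelled eyes with no other component, none of which the documents state. They do not show that bias will occur. The change is worth making because it is cheap, and because findings never recorded cannot be recovered later.

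**What to change.** On CRF 3, at every scheduled slit-lamp exam in both arms and whether or not an event is declared, record:

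- chamber depth as no touch, peripheral iris-cornea touch, touch to the pupil, or lens-cornea touch;
- hyphema as none, cells only, or layered with height in mm.

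In section 7.3, derive the shallow/flat chamber and hyphema components from these recorded levels and not from the investigator's event label. Report shallow and flat separately alongside the any-grade count. Pre-specify a sensitivity analysis restricted to the higher grades.

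The cost is two fields on a form already used at an examination already scheduled at every follow-up visit (Table 1), plus a little more analysis. The any-grade count is kept, so no events are lost. The examiner remains unmasked, so fixed levels reduce discretion but do not remove it.
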